6.4 INTERRUPTION OR DISCONTINUATION OF TREATMENT

Every subject has the right to refuse further participation in the study at any time and without providing reasons (see also Section 9.1.2). A subject's participation is to be terminated immediately upon request. The investigator should seek to obtain the reason and record this on the electronic case report form (eCRF).

Should the subject, during the course of the study, develop conditions, which would have prevented his/her entry into the study according to the safety related medical exclusion criteria, he/she must be withdrawn immediately.

The subject may be withdrawn from the study at any time at the discretion of the investigator for medical reasons and/or due to non-adherence to the treatment

Confidential

San Antonio, TX Protocol No. SAN007-02 Final Am 6: 18-Sept-2017

scheme and other duties stipulated in the study protocol. The reasons are to be fully documented on the eCRF.

In addition, the sponsor and the investigator reserve the right to end or suspend the study at any time (see Section 9.2.3).

6.5 WITHDRAWALS

The following medical and other reasons justify a premature termination, by subject or investigator, of any of the study products:

- Adverse event (including any SAE, clinically significant AE, intercurrent illness, or other medical condition that indicates to the investigator that continued participation is not in the best interest of the subject);
- Death;
- Lost to follow-up;
- Noncompliance with study medication dosing regimen, protocol requirements, or study-related procedures;
- Investigator discretion in case of occurrence of any medication condition, requirement for prohibited concomitant medication or treatment, or circumstances that would not allow the subject to adhere to protocol requirements;
- Pregnancy;
- · Study terminated by Sponsor;
- Withdrawal of consent;

If a subject withdraws from the study, all efforts will be made to complete a final evaluation. subjects discontinued due to an AE will be followed until the AE is resolved, a reasonable explanation is provided for the event, or the subject is referred to his/her own primary medical doctor. The specific AE in question will be recorded on the appropriate eCRF. All subjects who are withdrawn should complete protocol-specified withdrawal procedures.

6.6 WITHDRAWAL PROCEDURES

Protocol-specified withdrawal procedures are the same as those to be performed at the last study visit (Section 5.2.4).

6.7 SUBJECT REPLACEMENT

Subjects who prematurely discontinue the study may be replaced until 90 subjects have completed the study, or a total of 100 subjects have been enrolled, from the time of this amendment.

6.8 SUBJECT RE-SCREENING

Subjects previously denied entry into the study may be re-screened for eligibility once all enrollment criteria are met and issued a new subject number.

7. STUDY TREATMENT

7.1 DRUG PRODUCT (SAN007)

7.1.1 Formulation

The active ingredient under investigation in this study is East Indian Sandalwood Oil (EISO) in a cream for topical administration.

Formulation information for the investigational products is presented in Tables 7-1 and 7-2.

Table 7-1: Study Drug Information

Active ingredient	East Indian sandalwood oil (EISO)
	(5%, based on w/w)
Inactive ingredients	Purified water, Potassium Phosphate, Monobasic (USP), Sodium Hydroxide (NF), Sodium Lauryl Sulfate (NF/USP), Methylparaben (NF), Cetyl Alcohol (USP), Stearyl Alcohol (USP), Propolene Glycol (USP), t-Butyl Hydroquinone (TBHQ) (FCC), Propylparaben (NF).
Dosing schedule	Twice daily (bid) for 28 days. Topically.
Manufacturer	Pam Lewis & Associates Boerne, TX, USA
Packaging	60 gram (50 gram fill) white aluminum tube w/internal liner
Storage requirements	Store at controlled room temperature ^a (20°C to 25°C [68°F to 77°F])

a: Excursions are allowed between 15°C and 30°C (59°F and 86°F)

Table 7-2: Study Drug Information

Active ingredient	East Indian sandalwood oil (EISO) (10%, based on w/w)
Inactive ingredients	Purified water, Potassium Phosphate, Monobasic (USP), Sodium Hydroxide (NF), Sodium Lauryl Sulfate (NF/USP), Propolene Glycol (USP), Methylparaben (NF), Cetyl Alcohol (USP), Stearyl Alcohol (USP), Isopropyl Palmitate, NF, White Petrolatam, USP, Light Mineral Oil, NF, t-Butyl Hydroquinone (TBHQ) (FCC), Propylparaben (NF)
Dosing schedule	Twice daily (bid) for 28 days. Topically.
Manufacturer	Pam Lewis & Associates Boerne, TX, USA
Packaging	60 gram (50 gram fill) white aluminum tube w/internal liner
Storage requirements	Store at controlled room temperature ^a (20°C to 25°C [68°F to 77°F])

a: Excursions are allowed between 15°C and 30°C (59°F and 86°F)

Table 7-3: Placebo Information

Active ingredient	None
Inactive ingredients	Purified water, Potassium Phosphate, Monobasic (USP), Sodium Hydroxide (NF), Sodium Lauryl Sulfate (NF/USP), Propolene Glycol (USP), Methylparaben (NF), Cetyl Alcohol (USP), Stearyl Alcohol (USP), Isopropyl Palmitate, NF, White Petrolatam, USP, Light Mineral Oil, NF, t-Butyl Hydroquinone (TBHQ) (FCC), Propylparaben (NF).
Dosing schedule	Twice daily (bid) for 28 days. Topically.
Manufacturer	Pam Lewis & Associates Boerne, TX, USA
Packaging	60 gram (50 gram fill) white aluminum tube w/internal liner
Storage requirements	Store at controlled room temperature ^a (20°C to 25°C [68°F to 77°F])

a: Excursions are allowed between 15°C and 30°C (59°F and 86°F)

7.1.2 Packaging and Labeling

The study product labels will contain, at minimum, the following information:

- Sponsor name and address;
- Protocol number;
- Kit Number;
- Subject number (may be hand printed on the label);
- Product description;
- Lot number;
- Storage conditions;
- Investigator name (may be hand printed on the label);

- Expiry or retest date, if applicable;
- "Investigational use only. Keep out of reach of children"
- For topical application only. Apply only to atopic dermatitis, in treatment areas twice daily, morning and evening.

Study product will be provided individually. Only one study product container will be dispensed at one time to the subject, with additional tubes dispensed as needed.

7.1.3 Dosing Regimen

Subjects are to self-administer the treatment regimen according to the following schedule and order:

- Step 1. Thoroughly wash the treatment area with study-issued cleanser, tepid water, and a clean washcloth.
- Step 2. After gently patting the skin dry, apply the study medication to the target treatment area(s) as directed by the study staff. Study medication dosing is as follows: approximately 0.5 gm (approximately one fingertip, from the first knuckle to the tip of the finger) per 1% body surface area involvement (approximately the size of the palm of one's hand) should be applied to the treatment area. Be sure to apply the study medication morning and night, ≥ 8 hours in between doses, and wait until the area feels dry to the touch before covering with clothes.
- Step 3. Wash hands thoroughly to remove any traces of study medication and to prevent the accidental contact of study medication with nontreatment areas.

The site staff will be responsible for instructing subjects on the procedures for self-administration at home, with subjects applying first dose at Visit 1 Baseline. Subjects achieving complete symptom resolution will continue to apply study medication for the entire 28-day treatment period. Dose administration should be \geq 8 hours between doses.

7.1.4 Dose Modification

In the event the subject experiences a rash, or any other health issue in the treatment area during the study, the subject should be examined by the investigator. All AEs should be recorded in the electronic case report forms (eCRFs) and local skin reactions must be reported to the study coordinator and/or investigator.

If a subject experiences a new or worsening localized rash in the treatment area or generalized rash, the subject should contact the study site, cease study treatment, and report to the study center for examination.

Upon resolution of any rashes (localized or generalized), the subject may be rechallenged with study treatment under medical supervision by study personnel. The investigator or designee must stress the importance of applying the treatment regimen according to the instructions provided. In the absence of further rashes/skin irritations, study treatment may resume. If a rash or skin condition reappears, treatment should be stopped, subjects should report to the study physician, and they will be discontinued from the study.

Although there have been rare (<1%) reported instances of anaphylaxis in the literature, anaphylactic reaction is possible. If a subject suspects that he/she may be experiencing a severe, acute reaction, the subject should report to the nearest hospital Emergency Room, Urgent Care center, or call 911 or 000 for immediate treatment and stabilization. At that point, the subject should have final study assessments performed (if reasonable) and should be discontinued from the study.

Definition of Dose Limiting Toxicity

For this study, a dose-limiting toxicity is defined as any one or more of the following:

- · Any instance of anaphylaxis during treatment.
- Any instance of angioedema during treatment.
- Second instance of an allergic reaction following re-challenge by subjects who had only minimal redness or reaction during study treatment

Subjects should NOT be re-challenged if they experienced a generalized allergic reaction or a severe local reaction (e.g., severe erythema, blistering or swelling at the site of application).

7.1.5 Assignment to Treatment

7.1.5.1 Subject Numbering

Each subject who signs informed consent and photograph consent documents and successfully completes the screening procedures will be enrolled into the study.

Each subject will be assigned a unique subject number that will be used on all eCRFs.

7.1.5.2 Prior and Concomitant Therapy

All medications, including all prescription drugs, nonprescription drugs, and nutritional supplements, taken within 60 days prior to the start of the study will be recorded at the Screening Visit and updated as necessary at each subsequent visit.

San Antonio, TX Protocol No. SAN007-02

Final Am 6: 18-Sept-2017

Information regarding the total daily dose, route of administration, start and discontinuation dates, and indication are to be recorded on the Subject's eCRF.

Concomitant therapies that are not permitted at any time during the Subject's participation in the trial include, but are not limited to, isotretinoin, corticosteroids or retinoids (oral or topical), all immunosuppressive or immunomodulary medications (biologics), any medication being used off-label for the treatment of atopic dermatitis, and all other anti-atopic dermatitis medications.

In addition, no other treatments to the target treatment area(s) should occur during study participation.

7.2 TREATMENT COMPLIANCE

At each study visit, subjects will be questioned about compliance with the treatment schedule. Subjects who are consistently noncompliant (i.e., < 90% of required doses) will be counseled and may be withdrawn from the study.

Records of study product used will be kept. The products will be weighed prior to dispensation and at each study visit. Subjects will be asked to return all used, partially used, and empty products to the study site at the end of the study.

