- Update concomitant medications, including all prescription drugs, nonprescription drugs, and nutritional supplements.
- Query for treatment regimen compliance.
- Weigh and record the weight of the study medication, re-dispense existing, or dispense a new tube of study medication
- Calculate compliance. (i.e. Visit Day x 2 (applications per day) x EUA= expected usage). If Subject's actual compliance is ≤80% of expected compliance, reeducate and document in source.
- Photograph the treatment area(s).
- Review the directions for use of the study medication with the subject, and re-educate, if applicable.
- (Visit 2 [Day 7 \pm 2] only). Instruct the subject to return in one week for the next study visit with study drug.
- (Visit 3 [Day 14 ± 2] only). Remind the subject that there will be a follow up telephone call for Visit 4 (Day 21 ± 2)

de l'emporte	Visit 4 (Day 21 ± 2) Telephone Contact
	Query for adverse events.
fair and ear	 Update concomitant medications, to include all prescription drugs, nonprescription drugs, and nutritional supplements.
1 1 1 1 1	 Query for treatment regimen compliance.
8 1 1 1 1 X	 Instruct subject to return to the clinic for Visit 5 Final Visit on Day 28, with the study drug.
Final Visit	(Day 28 ± 2) Visit 5 Final Visit
	Query for adverse events.
n politica, et e	 Update concomitant medications including all prescription drugs, nonprescription drugs, and nutritional supplements.
	Query for treatment regimen compliance.
) 1 yes	Collect and weigh the study medication, and record the weight.
n je bjer e	 Calculate compliance. (i.e. Visit Day x 2 (applications per day) x EUA= expected usage) If Subject's actual compliance is ≤80% of expected compliance, re- educate and document in source.
i i i i i i i i i i i i i i i i i i i	 If subject is a female of childbearing potential, collect a urine sample and perform a □-human chorionic gonadotropin pregnancy test.
	 Administer the following assessments, in which only the treatment area(s) are to be evaluated: Investigator's Global Assessment (IGA), Tolerability and BSA.
	Administer the Eczema Area Severity Index (EASI).
	Photograph the treatment area(s).
made dans. Jan 1	 Instruct Subject to return to the clinic for another Study Visit only if study-related adverse events persist, or, in the Investigator's opinion, an additional Study Visit is warranted to ensure the subject's safety.
Follow-up Phone Contact	Day 35 (± 2 days) Telephone Contact

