Conlact	Query for status of AD since discontinuation of study

San Antonio, TX

Protocol No. SAN007-02 Final Am 6: 18-Sept-2017

	medication				
	 E.g. Has your condition been stable, improved, or worsened, since the discontinuation of study treatment? 				
Duration of Treatment and	The maximum duration of trial participation for each subject is up to 35 days:				
Trial Participation	7-day Screening Period (Day - 7)				
	28 ± 2 days Treatment (Visits 2 through 5)				
	Follow-up Call (Day 35)				
	Phone contact on Visit 4 (Day 21) and follow-up call (Day 35,) will be made with the subject.				
	If the subject's treatment is interrupted by illness or other circumstances, every attempt will be made to have the subject return to the clinic for a final visit. If the subject has remained compliant with the study medication, as determined by subject, and confirmed by product weight, if necessary, the subject will be allowed to continue the trial.				
Trial Drug, Dose and Mode of Administration	SAN007 treatment products will be provided by Santalis Pharmaceuticals, and the treatment regimen administered to the subject and explained to the LAR, if applicable.				
	The following treatment products will be provided to the subjects:				
	Cetaphil Daily Facial Cleanser- to be used on the face when washing.				
	Cetaphil Gentle Skin Cleanser- to be used on the body when showering.				
	AND STUDY DRUG LABELED WITH ONE OF THE FOLLOWING:				
	 5% SAN007 Cream - to be used morning and night, ≥ 8 hours between applications 				
	OR ION IN ION IO				
	 Placebo - to be used morning and night, ≥ 8 hours between applications 				
	OR				
	 10% SAN007 Cream - to be used morning and night, ≥ 8 hours between applications 				
	OR				
	 Placebo - to be used morning and night, ≥ 8 hours between applications 				

	The first treatment of SAN007 will be applied at the Visit 1 Baseline, then, the subject will be instructed on the procedure for self-administration at home.			
Trial Population	Up to 100 subjects, from the time of this amendment, at least 18 years of age, with a clinical diagnosis of atopic dermatitis meeting the criteria of an EASI score between 2-50 (Hanifin, 2001) with a BSA involvement of atopic dermatitis between 2%-15%, in the permitted treatment areas.			
Criteria for Evaluation	Subjects that receive one application of study medication will be included in the safety and tolerability analysis.			

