 (using only study-approved cleanser) and self-application of SAN007 study
 medication, subject to apply first dose in the office.
- Assess Tolerability immediately following study drug application.
- Weigh tube of SAN007, with cap on, immediately following first application
 and record weight prior to for dose. The difference between this weight
 and the pre-application weight is to be used as the expected estimated
 usage per application. (i.e. pre-application weight- post-application
 weight = expected usage per application (EUA)
- Photograph the treatment area(s).
- Instruct the subject, when bathing, to refrain from using any body wash, lotion or moisturizer, other than that which has been provided for the treatment areas during the treatment period.
- Instruct the subject to return with the study drug in one week for the next study visit.

Visits 2 (Day 7 [±2 days]) and 3 (Day 14 [±2 days])

The following procedures will be performed during Treatment Visit 2 and Visit 3:

- Query for adverse events.
- Administer the following assessments, in which only the treatment area(s) are to be evaluated: Investigator's Global Assessment (IGA), Tolerability and BSA.

- Administer the Eczema Area Severity Index (EASI).
- Update concomitant medications including all prescription drugs, nonprescription drugs, and nutritional supplements.
- Query for treatment regimen compliance.
- Weigh and record the weight of the study medication, then re-dispense existing, or dispense a new, tube of study medication
- Calculate compliance. (i.e. visit day x 2 (applications per day) x EUA= expected usage) If Subject's actual compliance is ≤80% of expected compliance, re-educate and document in source.
- Photograph the treatment area(s).
- Review the directions for use of the study medication with the subject, and re-educate if applicable.
- (Visit 2 [Day 7 \pm 2] only) Instruct the subject to return in one week for the next study visit, with their study drug.
- (Visit 3 [Day 14 ± 2] only) Remind the subject that the next visit will be a telephone follow-up Visit 4 (Day 21 ± 2)

Visit 4 Telephone Call (Day 21 [±2 days])

The following information will be collected from the subject during the Visit 4 telephone call:

- Query for adverse events.
- Update concomitant medications including all prescription drugs, nonprescription drugs, and nutritional supplements.
- Query for treatment regimen compliance.

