9.0 CONVENTIONS FOR CALCULATIONS AND TABULATIONS

Table 9.0 Conventions for Calculations and Tabulations

CONVENTION	DESCRIPTION
Age calculation	Age is calculated as an integer in years as the difference between the subject's date of informed consent and the date of birth. Specifically, if a subject's birthday has been reached by the informed consent date then age will be the difference in years, otherwise age will be the difference in years minus 1.
Baseline	Baseline is defined as assessments completed on Visit 1 (Day 1) prior to the administration of the study drug unless otherwise

CONVENTION	DESCRIPTION
	specified.
Study Day	Date of visit or evaluation – baseline date + 1
Percentage calculation	Percentages are calculated as 100*numerator/denominator. Rounding is not necessary because rounding is handled by the display format. Denominator is the total number of subjects in a column group unless otherwise specified.
AE counting: treatment emergence	An AE will be considered treatment emergent if it begins on or after the time of the first study treatment application. If the start date is the same as the date of first application (Day 1), the times are not present, or there is no indication that the AE began before dosing, the event will be considered treatment emergent.
AE counting: general summary	In summary displays, AEs are counted only once per subject within a category (e.g., over all and preferred term).
AE counting: summary by assessment	When AEs are summarized within levels of another AE assessment (e.g., causality or severity), AEs are counted once per subject at the worst level of the assessment (e.g., least complementary relationship or greatest severity). A missing or unknown value for the assessment will be considered worst.
Change from Baseline	current visit value – baseline visit value
Percent Change from Baseline	((current visit value —baseline visit value) / baseline visit value) x 100

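### The expected-usage formula counts more doses than are due by the visit (small effect), and withdrawing non-adherent subjects from the study gives up Day 28 and adverse event data that could be kept cheaply

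*Protocol*

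**What the plan says.** **Formula.** The synopsis gives "Visit Day x 2 (applications per day) x EUA= expected usage", and Protocol 5.2 repeats it for Visits 2, 3 and 5. EUA is the drop in tube weight at the first application, made in the clinic on Day 1. The action attached is: "If Subject's actual compliance is ≤80% of expected compliance, re-educate and document in source". SAP Table 9.0 defines Study Day as "Date of visit or evaluation – baseline date + 1", so the baseline visit is Day 1.

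**Withdrawal.** Protocol 7.2 has subjects questioned at each visit and tubes weighed, and then says: "Subjects who are consistently noncompliant (i.e., < 90% of required doses) will be counseled and may be withdrawn from the study". Protocol 6.4 lets the investigator withdraw a subject from the study "for medical reasons and/or due to non-adherence to the treatment" scheme. Protocol 6.5 lists noncompliance among the reasons that "justify a premature termination, by subject or investigator, of any of the study products", which is stopping product rather than leaving the study. For interrupted treatment, the synopsis uses compliance "as determined by subject, and confirmed by product weight, if necessary, the subject will be allowed to continue the trial".

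**After withdrawal.** Protocol 6.5 and 6.6 call for a final evaluation with the last-visit procedures. SAP 4.2 and 8.0 carry the last efficacy observation forward. Protocol 8.3.3 and SAP 3.3 treat a missing Day 28 observation as a major violation for the per-protocol set. SAP 7.1 captures non-serious AEs to the last application or exit, and serious AEs for 28 days after therapy stops.

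**The concern.** Two separate matters arise.

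(A) Multiplying the visit day by two counts every day from Day 1 to the visit day as a full two-dose day. Day 1 may hold only the office dose, and at a daytime visit the evening dose has not been made. The yardstick is therefore too long, and proportionally most so at the first follow-up visit. At stake is whether an adherent subject is recorded as falling short.

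(B) Leaving the study and stopping the cream are different events, but 7.2 and 6.4 let non-adherence lead to the first. At stake are observed Day 28 efficacy and non-serious AE follow-up, in a trial whose primary objective is safety (SAP 1.1.1).

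**Working it through.** The documents give no compliance percentage for an adherent subject, so there is no stated figure to reproduce.

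**Part A: inputs and assumptions.** Dosing is twice daily (Protocol 3.1). The first dose is in the office on Day 1 (5.2). Assumed: a daytime visit before the evening dose, every application weighing exactly one EUA, and usage counted from the full tube so that the office dose is included.

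For a visit on Day d with nothing missed, Day 1 holds 1 or 2 applications, Days 2 to d-1 hold 2 each, and the visit day holds 0 or 1 before weighing. The total is 2d-3, 2d-2 or 2d-1. The protocol divides by 2d; the correction divides by 2(d-1).

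| Visit | Applications made | Current divisor | Current score | Corrected divisor | Corrected score |
|---|---|---|---|---|---|
| Day 7 | 11, 12, 13 | 14 | 78.6, 85.7, 92.9% | 12 | 91.7, 100.0, 108.3% |
| Day 14 | 25, 26, 27 | 28 | 89.3, 92.9, 96.4% | 26 | 96.2, 100.0, 103.8% |
| Day 28 | 53, 54, 55 | 56 | 94.6, 96.4, 98.2% | 54 | 98.1, 100.0, 101.9% |

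At visits on the nominal day, only the lowest Day 7 case reaches 80%: one dose on Day 1 and no morning dose before weighing.

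How this moves with the assumptions:

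- *Visit Day read as the actual day.* A Day 5 visit gives 7, 8 or 9 of 10 = 70.0, 80.0 or 90.0%, so two of the three cases are flagged. On Day 6 the lowest case is 9/12 = 75.0%. On Day 8 it is 13/16 = 81.25%, so none is flagged. With the corrected count, the lowest in-window value is 7/8 = 87.5%, on Day 5.
- *Visit Day read as the nominal day.* Visit 2 on Day 5 gives 7 to 9 of 14 = 50.0 to 64.3%, while on Day 9 it gives 15 to 17 of 14 = 107.1 to 121.4%. Visit 3 on Day 12 gives 21 to 23 of 28 = 75.0 to 82.1%. The error can grow, vanish or reverse.
- *Usage counted from the tube weight after the office dose.* Day 7 becomes 10 to 12 of 14 = 71.4 to 85.7% now, and 10 to 12 of 12 = 83.3 to 100% corrected.
- *Dose size.* With 12 applications at Day 7, the 80% line is 0.8 x 14 = 11.2 EUA. It is reached if applications average 11.2/12 = 93.3% of EUA, or 6.7% under. Corrected, it is 0.8 x 12 = 9.6 EUA, and 9.6/12 = 80.0%, or 20.0% under.

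Usage must be summed over tubes: at the minimum 2% BSA the dose is 1 g, so 53 to 55 applications use 53 to 55 g, more than one 50 g fill.

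**Part B: withdrawal before the Day 28 window.** Scheduled post-baseline efficacy assessments fall at Visits 2, 3 and 5, and AE queries at Visits 2, 3, 4 and 5. If exit coincides with Visit 3, one of three efficacy looks and two of four AE queries are lost. If the exit evaluation is a separate later visit, its data enter the carry-forward (SAP 4.1), so less is lost.

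- Lost: the observed Day 28 result, per-protocol membership, and non-serious AE capture after exit.
- Kept: the FAS (one dose and one post-baseline assessment), the Safety Set, earlier visits for the any-time responder endpoints, and SAEs for 28 days.

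**The case against.** The strongest reply is about size. The formula triggers only re-education, and sites already review the directions with every subject at Visits 2 and 3. With visits on the nominal day, only one corner case is caught. Tube weight is a coarse measure anyway: dosing is approximate (7.1.3), new lesions may be treated (7.3.1), and SAP 5.2 accepts values above 100%. Withdrawal under 7.2 is optional, comes with counselling, and requires noncompliance to be consistent. An exit evaluation is attempted, the lost AE queries cover off-drug days, and discontinued subjects may be replaced (6.7). The analysis is descriptive and unpowered (8.2, 8.4.4). Keeping subjects after stopping treatment is partly a design preference, and it gives an off-drug subject another chance to meet an any-time endpoint.

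Nearly all of this stands, and it keeps the point small. It does not make the count right, and it does not show that anything is gained by ending follow-up along with treatment.

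A reader might infer more: that 7.2 uses the 5.2 formula, so that a fully adherent subject scoring 78.6% at Day 7 and 89.3% at Day 14 could be withdrawn. The documents do not support that. Section 7.2 speaks of required doses, begins from questioning, sets a different threshold and makes no reference to the formula. The synopsis has a 90% rule based on product usage, but it governs inclusion in the efficacy analysis, not withdrawal.

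**Conclusion.** (A) The formula is wrong as written, with little consequence. For a subject who missed nothing it understates compliance by 7.1 to 21.4 points at an exact Day 7 visit (100 minus 92.9 and 78.6) and by 1.8 to 5.4 points at Day 28. This assumes EUA-sized doses, a daytime visit and the office dose counted. The effect is some unneeded re-education, chiefly at Visit 2.

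(B) Allowing withdrawal from the study for non-adherence is a discretionary rule that can be improved cheaply. It is not an error. The documents give no count of affected subjects and I assume none; the effect on results is probably small.

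Two further inferences should be resisted. The overcount does not push adherent subjects out of the per-protocol set: the SAP cut is 60% of average usage over participation, and the exact-Day-28 score is at least 94.6%. Nor do the documents say that the formula caused the change in that cut from 90% to 60%. Section 7.2 leaves the counting of required doses and the meaning of consistent noncompliance open, and SAP 5.2 leaves the days in a period open. These are missing details, not errors, and the conclusion does not rest on them.

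**What to change.** 1. Synopsis and Protocol 5.2: set expected usage to (actual Visit Day - 1) x 2 x EUA, with usage cumulated from the full first tube over all tubes dispensed. Keep the 80% re-education trigger.
2. Protocol 7.2, 6.4 and 6.5: let noncompliance lead to counselling and, at most, to stopping study treatment. Keep the subject in the scheduled visits and AE queries through Day 28.
3. SAP 7.1: extend non-serious AE capture to Day 28 for these subjects, because the present text can end it at the last application.

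The cost is wording in the synopsis and four protocol sections, and one SAP sentence. Weights and dates are already collected, and no visits are added to the schedule. The real downside is some off-drug data in the FAS, including in the any-time responder endpoints; the report should identify these subjects.
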